13.0 CRITERIA FOR REMOVAL FROM STUDY

- Ineligibility of the patient as defined in inclusion/exclusion criteria
- Significant protocol violation
- Non-compliance of the patient
- Unacceptable toxicity which in the judgment of the investigator and/or treating physician renders further treatment on protocol contrary to the patient's best medical interest.
- Refusal of the patient to continue treatment and/or observation
- Unrelated medical illness or complication that increases the risk of protocol therapy to unacceptable levels.
- Progression of disease
- Decision by the Investigator that termination is in the patient's best medical interest.
- Loss to follow-up
- Death of the patient

14.1 BIOSTATISTICS

14.2 Study Endpoints

The two major objectives of this study are: (1) to determine the maximum tolerated dose of intravenous clofarabine using the schedule outlined above in patients with relapsed T- and NK-cell lymphomas and (2) to determine the response rate at this defined dose.

14.3 Study Design

To accomplish the first objective, an accelerated titration design will be used for the first patient. The next patient can be treated at the next dose level using the accelerated titration design if the currently treated patient does not have the following: 1) a grade 2 non-hematologic toxicity, or 2) a delay in the recovery of platelets or neutrophils at the day 22 ± 2 day evaluation.

If either of these criteria has been met (listed above), a standard titration scheme will be used where groups of at least three patients will be treated with escalating doses of clofarabine. A modified Fibonacci design was used to determine the size of the dose escalations.

Regardless of whether an accelerated or standard titration design is used, a patient cannot be enrolled to the next dose level (next cohort) until all patients within the current cohort satisfy one of the following: 1) the patient is off study, or 2) the patient has started the next cycle of clofarabine.

14.4 Dose-Escalation of clofarabine

Patients will be entered on the study and treated with clofarabine at an escalating dose as defined in section 9.2. Dose escalation will proceed as follows:

14.4.1 Accelerated titration design

- The next patient will be treated at the next dose level, if the patient does not have either: 1) a grade 2 non-hematologic toxicity, or 2) a delay in the recovery of platelets or neutrophils at the day 22 ± 2 day evaluation.

If the above criteria have not been met, the next patient will be enrolled at the **same** dose level using the standard titration design. See section 14.3.2.

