9.3 Clofarabine

Clofarabine will be infused intravenously over 1 hour and will be administered daily for 3 consecutive days. In the phase I portion of this study, the dose levels will be determined by the dose escalation schema in Table 9.0. Cycles will be repeated as early as day 22 ± 2 days or up to 2 weeks later (or 36 ± 2 days) if the patient meets retreatment criteria as defined in section 9.4.

Table 9.0 Dose Escalation Schema

Dose Level	Dose (mg/m ² /day)	% Increase	Multiple of Initial Dose
1	4	-	-
2	8	100	2.0 n
3	13.2	67	3.3 n
4	20	50	5.0 n
5	28	40	7.0 n
6	36	33	9.0 n
7	49	28	12.3 n

Refer to Section 14.1 for more details regarding dose escalation. Once the MTD of clofarabine has been identified, the remainder of the patients will be accrued to the phase II portion of the study.

Sponsor: Memorial Sloan-Kettering Cancer Center
IRB Protocol

IRB#: 06-065A(4)

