9.5 Re-treatment criteria

Patients will receive additional cycles of clofarabine as long as they meet the following criteria **at the time of re-treatment:**

- $ANC \geq 1000$ cell/ μ l (or $ANC \geq 500$ / μ l for patients who were enrolled at this level in the phase II portion of the trial only)
- Platelet $\geq 75,000$ / μ l (or platelet $\geq 50,000$ / μ l for patients who were enrolled at this level in the phase II portion of the trial only)
- Non-hematologic toxicity: if the toxicity is less severe than a grade 4 infection and/or a grade 4 hemorrhage, and it resolves to \leq grade 1 or baseline as per CTCAE v3.0 toxicity criteria at the time of retreatment.

Repeat cycles of clofarabine are administered on approximately a 21 day schedule unless the patient does not meet re-treatment criteria as defined above. For those patients who do not meet the above parameters at the day 22 ± 2 evaluation, their next cycle of therapy may be held up to 2 weeks. After any treatment delay, the patient will be re-evaluated the following week (up to day 36 ± 2 days). If the patient meets re-treatment criteria at the next evaluation, the next cycle of clofarabine will be administered at the full dose. If the patient does not meet re-treatment criteria at both the day 29 ± 2 and the day 36 ± 2 evaluation, this patient will be **removed** from the study **unless there has been a prior documented response (CR or PR) to therapy.**

**Sponsor: Memorial Sloan-Kettering Cancer Center
IRB Protocol**

IRB#: 06-065A(4)

In these cases, patients must meet all of the criteria defined in section 9.8. The dose of clofarabine will then be adjusted accordingly.

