14.4.2 Standard titration design

**Sponsor: Memorial Sloan-Kettering Cancer Center
IRB Protocol**

IRB#: 06-065A(4)

Refer to section 14.4 for the definition of DLT and MTD.

- If none of the initial three patients in a cohort experience dose-limiting toxicity (DLT), then a new cohort of three patients will be treated at the next higher dose level.
- If one of the three patients in a cohort experiences DLT, then up to three additional patients will be treated at the same dose level. Escalation will continue if only one of the six patients experiences DLT.
- If two or more patients in a cohort experience DLT, then the maximum tolerated dose (MTD) will have been exceeded, and no further dose escalations will occur. The previous dose level will be considered the MTD.
- If only three patients were treated at a dose level under consideration as the MTD, then up to three additional patients will be accrued. If no more than one of the six patients at that dose level experience DLT, then that dose level will be confirmed as the MTD. If two or more patients in that cohort experience DLT, then the previous dose level will be studied in the same fashion.

Accelerated Titration	
Number of Subjects with Drug Related DLT (Grade 2 non-hematologic toxicity or delay in platelet or neutrophil recovery at day 22) at a Given Dose Level	Dose Escalation Rules
0 of 1	Next patient can be treated at the next higher dose level
1 of 1	Convert to standard titration with this dose level and enroll 2 more subjects at this dose level
Standard Titration	
Number of Subjects with Drug Related DLT (as Defined in Section 14.4) at a	Dose Escalation Rules

**IRB
PB**

Amended: 8/26/08

**Sponsor: Memorial Sloan-Kettering Cancer Center
IRB Protocol**

IRB#: 06-065A(4)

Given Dose Level	
0 of 3	Next cohort of 3 subjects treated at the next higher dose level
1 of 3	3 more subjects are treated at that same dose level
≥ 2 of 3	Dose escalation stops and dose level is considered the Maximum Administered Dose (MAD). 3 more subjects will be added to the next lower dose level, unless 6 subjects have already been treated at that dose level
1 of 6	Next cohort of 3 subjects treated at the next higher dose level
> 2 of 6	Dose escalation stops and dose level is considered the Maximum Administered Dose (MAD). 3 more subjects will be added to the next lower dose level, unless 6 subjects have already been treated at that dose level
≤ 1 of 6 at the highest dose level below MAD	Maximum Tolerated Dose

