14.4.3 Observation period

Regardless of whether an accelerated or standard titration design is used in the phase I portion of the trial, a patient cannot be enrolled to the next dose level (next dose level) until all patients within the current cohort satisfy one of the following: 1) the patient(s) are off study, or 2) the patient(s) have started the next cycle of clofarabine.

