14.5 Definitions of DLT and MTD

DLT is defined as any of the following:

- **≥ Grade 2 thrombocytopenia (platelet < 75,000) lasting ≥ 36 ± 2 days from first day of clofarabine infusion,**
- **≥ Grade 3 non-hematologic toxicity according to NCI's CTCAE v 3.0**

MTD is defined as the highest dose studied for which the incidence of DLT is less than 33%. The percentage of patients who experience toxicity at each dose level will be calculated, with a 95% confidence interval.

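### The accelerated-titration trigger says grade 2, not grade 2 or higher, so read literally a lone grade 3 or 4 toxicity does not stop escalation

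*Combined protocol and SAP*

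**What the plan says.** The rule for leaving one-patient cohorts is stated three times.

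- Section 14.3 allows the next level if the current patient "does not have the following: 1) a grade 2 non-hematologic toxicity" and has no delay in platelet or neutrophil recovery at the day-22 evaluation.
- Section 14.4.1 repeats it: "The next patient will be treated at the next dose level, if the patient does not have either: 1) a grade 2 non-hematologic toxicity", with the same count-recovery condition.
- The accelerated part of the rule table in Section 14.4.2 labels its count as drug-related DLT and defines that in its own parenthesis: "Grade 2 non-hematologic toxicity or delay in platelet or neutrophil recovery at day 22". For 0 of 1, the action is "Next patient can be treated at the next higher dose level". For 1 of 1, the trial converts to standard titration at the same dose.

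None of the three says ≥ or an equivalent. Section 14.5 does use ≥ in both of its DLT criteria, one of which is ≥ "Grade 3 non-hematologic toxicity according to" CTCAE v3.0.

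Sections 14.3 and 14.4.3 also hold enrollment at the next level until every patient in the current cohort meets one of two conditions: "1) the patient(s) are off study, or 2) the patient(s) have started the next cycle of clofarabine".

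**The concern.** A stopping threshold should catch everything at least as bad as the threshold. As worded, a grade 2 event ends acceleration, while a lone grade 3 or 4 event does not. In the one-patient stage this trigger is the only stated toxicity test for going up a level, so a gap in it is not covered by a second test.

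What is at stake is the dose given to the next patient. The early steps are the largest in relative terms. The starting dose, at 12 mg/m² per week, is already slightly above the 10 mg/m² per week reported as the earlier MTD in solid tumors and lymphoproliferative disorders (Section 5.2). Section 7.0 names three recruiting centers, so the rule should not depend on each reader inferring what was meant.

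**Working it through.** **1. The plan's own figure.** Table V (Section 14.4.2) is the only escalation probability given, and it covers the standard phase. For 3+3, P(escalate) = (1−p)³ + 3p(1−p)² × (1−p)³. At p = 0.10, 0.20, 0.30, 0.40, 0.50 and 0.60 this gives 0.906, 0.709, 0.494, 0.309, 0.172 and 0.082. The stated values are 0.91, 0.71, 0.49, 0.31, 0.17 and 0.08, so all six match. Nothing below changes them. No figure is given for the accelerated stage.

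**2. Literal rule against corrected rule.** Cross the recorded non-hematologic toxicity (three classes) with count recovery at day 22 (yes or no). The literal rule escalates if no grade 2 is recorded and counts have recovered. The corrected rule escalates if no grade ≥ 2 is recorded and counts have recovered.

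| Recorded non-hematologic toxicity | Counts recovered | Literal | Corrected |
|---|---|---|---|
| Grade ≤ 1 only | Yes | Escalate | Escalate |
| Grade ≤ 1 only | No | Convert | Convert |
| Any grade 2 | Yes | Convert | Convert |
| Any grade 2 | No | Convert | Convert |
| Grade 3–4 only | Yes | **Escalate** | **Convert** |
| Grade 3–4 only | No | Convert | Convert |

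The rules differ in one case of six. This counts logical cases; it is not a risk.

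**3. Does another rule block that case?**

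- *DLT definition.* The rule table points to it only in the standard-titration heading. (The table cites Section 14.4; in the body the definition is headed 14.5.) The accelerated heading supplies its own parenthesis.
- *Standard rules.* These are written for cohorts of three or six, not for a lone patient.
- *Observation hold.* Section 9.5 sends the patient to one of the two conditions that end it. Re-treatment is allowed "if the toxicity is less severe than a grade 4 infection and/or a grade 4 hemorrhage, and it resolves to" grade 1 or baseline, so a grade 3 event that settles permits cycle 2. A grade 4 infection or hemorrhage, or an event still unresolved at days 29 and 36, fails re-treatment and leads to removal from study. The hold therefore delays escalation without preventing it.

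**4. Dose consequence.** In Section 9.3, "the dose levels will be determined by the dose escalation schema in Table 9.0". In the differing case the next patient receives the following:

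| Event at level | Corrected (mg/m²/d) | Literal (mg/m²/d) | Ratio | Extra per 3-day cycle (mg/m²) |
|---|---|---|---|---|
| 1 | 4 | 8 | 2.00 | 3 × 4 = 12 |
| 2 | 8 | 13.2 | 1.65 | 3 × 5.2 = 15.6 |
| 3 | 13.2 | 20 | 1.52 | 3 × 6.8 = 20.4 |
| 4 | 20 | 28 | 1.40 | 3 × 8 = 24 |
| 5 | 28 | 36 | 1.29 | 3 × 8 = 24 |
| 6 | 36 | 49 | 1.36 | 3 × 13 = 39 |

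**5. Frequency.** Let a be the probability of any recorded grade 2, b the probability of grade 3–4 with no grade 2 recorded, and h the probability of delayed counts, taken as independent of grade. The chance of escalating is (1−a)(1−h) under the literal rule and (1−a−b)(1−h) under the corrected rule, a difference of b(1−h). The documents give none of these inputs. As an assumption only, with a = 0.20 and h = 0, the chance falls from 0.80 to 0.75 if b = 0.05, to 0.70 if b = 0.10 and to 0.60 if b = 0.20. The conclusion does not rest on these values.

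**The case against.** The strongest reply is that the text already closes the gap. The accelerated table counts drug-related DLTs, Section 14.4.2 opens by pointing to the DLT definition, and Section 14.5 makes any grade 3 or higher non-hematologic event a DLT without limiting that to standard titration. On this reading the parenthesis only lowers the bar for single-patient cohorts, and a grade 3 or 4 event is 1 of 1. Section 1.0 also describes acceleration as running until toxicity criteria are met, which is threshold language.

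This is good evidence of intent, but it does not settle the wording. Sections 14.3 and 14.4.1 state the trigger without mentioning DLT, and the pointer to the definition stands under the standard-titration heading. A reader following Section 14.4.1 alone would find escalation permitted.

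Four further points stand as limits:

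- The case is narrow. A severe event that resolves may well pass through a recorded grade 2, which meets the literal trigger; so do delayed counts.
- The dose ratios are the planned steps of Table 9.0. They measure the consequence in the affected case, not how often it arises. The upper steps apply only if single-patient titration lasts that long, and Section 5.2 predicts DLT around the third level.
- Non-hematologic toxicity was infrequent and mild in the earlier solid-tumor and lymphoproliferative patients. Grade 3–4 infection occurred in 94 of 377 patients elsewhere, but across doses of 2 to 70 mg/m²/d in other settings, so neither gives a rate for this schedule.
- SAE reporting within 5 days and committee monitoring make unnoticed escalation less plausible. They do not replace an escalation rule.

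**Conclusion.** The concern holds: the rule is wrong as written. Under the literal wording in all three places, a lone patient with only a grade 3 or 4 non-hematologic event and recovered counts does not stop acceleration, and no other stated escalation rule clearly does.

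The result assumes a one-patient cohort, no separately recorded grade 2 event, and count recovery by day 22. Within that case the next patient could receive 1.29 to 2.0 times the intended dose: twice after an event at level 1, 1.65 times at level 2 and 1.52 times at level 3. No event rate, effect on the MTD or change to Table V is claimed. This looks like a drafting omission rather than a deliberate choice. It should still be corrected, because it sits in a safety threshold and as worded gives the wrong action.

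**What to change.** In Sections 14.3 and 14.4.1 and in the accelerated heading of the Section 14.4.2 table, write: ≥ grade 2 non-hematologic toxicity (CTCAE v3.0).

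As an editorial clean-up only, reword the follow-on sentence in Section 14.4.1, where the word criteria is used in a different sense from Section 14.3 although both lead to the same action. Suggested wording: If either toxicity occurs, the next patient will be enrolled at the same dose level using the standard titration design.

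The cost is three inserted signs, with the grading reference, and one reworded sentence. No patients, visits or data are added.

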14.4.2 Standard titration design

**Sponsor: Memorial Sloan-Kettering Cancer Center
IRB Protocol**

IRB#: 06-065A(4)

Refer to section 14.4 for the definition of DLT and MTD.

- If none of the initial three patients in a cohort experience dose-limiting toxicity (DLT), then a new cohort of three patients will be treated at the next higher dose level.
- If one of the three patients in a cohort experiences DLT, then up to three additional patients will be treated at the same dose level. Escalation will continue if only one of the six patients experiences DLT.
- If two or more patients in a cohort experience DLT, then the maximum tolerated dose (MTD) will have been exceeded, and no further dose escalations will occur. The previous dose level will be considered the MTD.
- If only three patients were treated at a dose level under consideration as the MTD, then up to three additional patients will be accrued. If no more than one of the six patients at that dose level experience DLT, then that dose level will be confirmed as the MTD. If two or more patients in that cohort experience DLT, then the previous dose level will be studied in the same fashion.

Accelerated Titration	
Number of Subjects with Drug Related DLT (Grade 2 non-hematologic toxicity or delay in platelet or neutrophil recovery at day 22) at a Given Dose Level	Dose Escalation Rules
0 of 1	Next patient can be treated at the next higher dose level
1 of 1	Convert to standard titration with this dose level and enroll 2 more subjects at this dose level
Standard Titration	
Number of Subjects with Drug Related DLT (as Defined in Section 14.4) at a	Dose Escalation Rules

**IRB
PB**

Amended: 8/26/08

**Sponsor: Memorial Sloan-Kettering Cancer Center
IRB Protocol**

IRB#: 06-065A(4)

Given Dose Level	
0 of 3	Next cohort of 3 subjects treated at the next higher dose level
1 of 3	3 more subjects are treated at that same dose level
≥ 2 of 3	Dose escalation stops and dose level is considered the Maximum Administered Dose (MAD). 3 more subjects will be added to the next lower dose level, unless 6 subjects have already been treated at that dose level
1 of 6	Next cohort of 3 subjects treated at the next higher dose level
> 2 of 6	Dose escalation stops and dose level is considered the Maximum Administered Dose (MAD). 3 more subjects will be added to the next lower dose level, unless 6 subjects have already been treated at that dose level
≤ 1 of 6 at the highest dose level below MAD	Maximum Tolerated Dose

Table V provides the probabilities of dose escalation based on true risk of toxicity for the standard phase dose escalation scheme.

Table V. Probability of Dose Escalation.

Risk of Toxicity	Probability of Escalation
0.10	0.91
0.20	0.71
0.30	0.49
0.40	0.31
0.50	0.17
0.60	0.08

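### The dose-escalation table stops a six-patient cohort only above 2 DLTs, while the text stops at 2, so exactly 2 of 6 has no row in the table

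*Combined protocol and SAP*

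**What the plan says.** Section 14.4.2 (Standard titration design) states the rules first as bullets and then as a table.

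- **Stopping, third bullet:** "If two or more patients in a cohort experience DLT, then the maximum tolerated dose (MTD) will have been exceeded".
- **Escalation after expansion to six, second bullet:** "Escalation will continue if only one of the six patients experiences DLT".
- **Confirming or stepping back from a candidate MTD, fourth bullet:** "If no more than one of the six patients at that dose level experience DLT, then that dose level will be confirmed as the MTD". Otherwise, "If two or more patients in that cohort experience DLT, then the previous dose level will be studied in the same fashion".
- **Rules table, standard titration:** the left-hand entries are `0 of 3`, `1 of 3`, `≥ 2 of 3`, `1 of 6`, `> 2 of 6` and a final MTD row, "≤ 1 of 6 at the highest dose level below MAD". The `> 2 of 6` row carries two instructions: stop escalating, and add three patients at the next lower level unless six have already been treated there.

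Table V, which follows, "provides the probabilities of dose escalation based on true risk of toxicity". Section 14.5 defines the MTD as "the highest dose studied for which the incidence of DLT is less than 33" percent.

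**The concern.** The bullets put the six-patient stopping threshold at 2 DLTs and the table puts it at 3. The table's six-patient rows cover 1 (escalate), 3 or more (stop and step down) and at most 1 (MTD). They give no action for exactly 2. Because the same row holds the step-down instruction, the gap also affects a candidate MTD that is expanded to six and ends with 2 DLTs.

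This is the boundary that stops escalation for toxicity. Section 7.0 names three recruiting centers, and a table of this kind is what staff consult when a cohort completes. A reader who takes 3 of 6 as the stopping point and escalates after 2 of 6 would treat patients above a dose that the text regards as exceeding the MTD. Each step up in Table 9.0 (Section 9.3) raises the dose by 28% to 100%. The harm would be that extra exposure. A dose with 2 of 6 DLTs still could not be named the MTD, because the MTD row and the Section 14.5 definition both exclude it.

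**Working it through.** **Inputs.** The escalation rules come from the bullets and table in Section 14.4.2, the printed escalation probabilities from Table V, and the 33% limit from Section 14.5. Let p be the true DLT risk and q = 1 − p. Patients are taken as independent, and expansion adds three patients, as the `1 of 3` row directs.

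**Step 1: reproduce Table V.** If 2 of 6 stops escalation, there are two routes upward: 0 of 3, or 1 of 3 followed by 0 of the next three.

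P(escalate) = q³ + 3pq² × q³

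If 2 of 6 also escalated, a third route would be added: 1 of 3 followed by 1 of the next three, with probability (3pq²)².

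| p | q³ | 3pq² × q³ | Sum, 2 of 6 stops | Table V | (3pq²)² | Sum, 2 of 6 escalates |
|---|---|---|---|---|---|---|
| 0.10 | 0.729 | 0.177 | 0.906 | 0.91 | 0.059 | 0.965 |
| 0.20 | 0.512 | 0.197 | 0.709 | 0.71 | 0.147 | 0.856 |
| 0.30 | 0.343 | 0.151 | 0.494 | 0.49 | 0.194 | 0.689 |
| 0.40 | 0.216 | 0.093 | 0.309 | 0.31 | 0.187 | 0.496 |
| 0.50 | 0.125 | 0.047 | 0.172 | 0.17 | 0.141 | 0.313 |
| 0.60 | 0.064 | 0.018 | 0.082 | 0.08 | 0.083 | 0.165 |

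The first sum rounds to Table V at all six risks and the second at none. Table V was therefore computed with 2 of 6 as a stop.

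**Step 2: check the MTD definition.** 1/6 = 16.7% is below 33%, and 2/6 = 33.3% is not. This agrees with the MTD row, which allows at most 1 of 6.

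**Step 3: how often the missing row is needed after 1 of 3.** Given 1 DLT in the first three, the final count depends on the next three.

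| p | 1 of 6: q³ | 2 of 6: 3pq² | 3 or more of 6: 1 − q³ − 3pq² |
|---|---|---|---|
| 0.20 | 0.512 | 0.384 | 0.104 |
| 0.30 | 0.343 | 0.441 | 0.216 |
| 0.40 | 0.216 | 0.432 | 0.352 |

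At risks 0.30 and 0.40, exactly 2 of 6 is the most likely result of an expanded cohort. Per dose level started, the probability of arriving there by this route is (3pq²)² = 0.147, 0.194 and 0.187 at risks 0.20, 0.30 and 0.40.

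**Step 4: the step-down route.** A level with 0 of 3 that is later expanded as the candidate MTD ends at 2 of 6 if two of the next three have a DLT, with probability 3p²q:

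- p = 0.30: 3 × 0.09 × 0.70 = 0.189
- p = 0.40: 3 × 0.16 × 0.60 = 0.288

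**The case against.** The strongest reply is that the decision rule is not missing. The second bullet does not allow escalation at 2 of 6, the third stops, and the fourth steps down. The table's only six-patient escalation row is `1 of 6`, so the table does not authorize escalation at 2 either. On this view the cell is a typographical slip, and under the written rules the escalation probability does not change. This stands as far as it goes: the rise from 0.49 to 0.69 is an upper bound that applies only if an absent row is taken as permission. It does not remove the conflict between two stated thresholds in one section.

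A second point is that the bullet speaks of up to three additional patients. If patients enter one at a time and entry stops at the second DLT, the second DLT falls on the sixth patient with probability pq² = 0.30 × 0.49 = 0.147 at risk 0.30, not 0.44. The 0.44 does assume full expansion, which is what the table's `1 of 3` row prescribes. Stopping early would not help the table, since it has no row for 2 of 4 or 2 of 5 either.

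Third, an underlined > can lose its underline when a PDF is converted to text, so the source may already read ≥. That cannot be ruled out. However, `≥ 2 of 3` and the ≤ sign in the MTD row are intact in the same table, so the cell is taken as printed.

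**Conclusion.** The concern holds. As printed, the six-patient stop row conflicts with the text of its own section and leaves exactly 2 of 6 without an instruction, both for stopping escalation and for stepping down. The intended threshold is not in doubt: the bullets, the MTD row, the 33% definition and Table V all give 2 or more of 6.

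The gap falls on a frequent outcome, 38% to 44% of cohorts expanded after 1 of 3 at DLT risks of 0.20 to 0.40, or 15% to 19% of dose levels started. These figures assume independent patients and full expansion to six. The possible effect on conduct is bounded by a rise in escalation probability from 0.49 to 0.69 at risk 0.30 and from 0.31 to 0.50 at risk 0.40, and only if the table is misread against the text. Because this is a toxicity stopping boundary and the correction costs almost nothing, it must be fixed.

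**What to change.** Check the cell against the approved protocol. If it reads `> 2 of 6` there, change it to `≥ 2 of 6`. The bullets, Table V, the MTD row and the MTD definition stay as they are. The cost is one character in one table cell, with no added patients and no change to the design's operating characteristics.

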In this study, the starting dose of 4 mg/m²/d for 3 consecutive days was chosen based on the MTD for both solid and lymphoproliferative disorders. In all of the published clofarabine trials, patients were treated for 5 consecutive days. With a MTD of 2 mg/m²/d, patients with solid and lymphoproliferative disorders received a weekly total dose of 10 mg/m²/wk. With a starting dose of 4 mg/m²/d for 3 consecutive days, patients will receive 12 mg/m²/wk. We predict that the DLT will occur around the third dose level since it is defined differently compared to the prior trials. The DLT, in this study, is defined in terms of delayed count recovery rather than grade 3 or 4 myelosuppression at any time following treatment.

IRB
PB

Amended: 8/26/08

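### The 14.4.2 expansion rule brings a level cleared in accelerated titration to four patients, two short of the six its own MTD criterion needs

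*Combined protocol and SAP*

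**What the plan says.** All references are to the combined protocol and SAP, by the section numbers printed in the body.

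- **Accelerated titration (14.4.2 table).** With no trigger toxicity in the single patient at a level: "Next patient can be treated at the next higher dose level". With a trigger toxicity: "Convert to standard titration with this dose level and enroll 2 more subjects at this dose level".
- **Expansion after a MAD (both MAD rows of the table).** "3 more subjects will be added to the next lower dose level, unless 6 subjects have already been treated at that dose level".
- **MTD row of the table.** The MTD is the level with "≤ 1 of 6 at the highest dose level below MAD".
- **Third bullet of 14.4.2.** Two or more DLTs in a cohort stop escalation, and the level below is taken as the MTD. No number of patients is attached.
- **Fourth bullet of 14.4.2.** "If only three patients were treated at a dose level under consideration as the MTD, then up to three additional patients will be accrued". The level is confirmed if at most one of six has a DLT. If two or more do, "then the previous dose level will be studied in the same fashion".
- **14.5.** "MTD is defined as the highest dose studied for which the incidence of DLT is less than 33" percent, with no minimum number of patients.
- **14.6.** Stage 1 of phase II has 8 patients, described as two beyond those already treated at the MTD in phase I. That implies six.

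**The concern.** The number to add (three) is right only for a level that already holds three patients. A level cleared in accelerated titration holds one, and conversion fills only the level where the trigger occurred. No rule goes back to fill the levels below. If the conversion level proves to be the MAD, the level below it is brought to four patients, while the table and the fourth bullet judge it on six.

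Finding the MTD is the first major objective (14.2), and it is the dose for all of phase II. On this path the plan gives the team rules that disagree about how many patients support that dose: one or more under the third bullet, any number under 14.5, four by the expansion count, six by the MTD row. The choice would then be made during the trial, with the DLT data in view.

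**Working it through.** **1. The plan's own figures.** Table V follows from the 3+3 rule: P(escalate) = (1−p)³ + 3p(1−p)²·(1−p)³. At p = 0.10 to 0.60 this gives 0.906, 0.709, 0.494, 0.309, 0.172 and 0.082, matching the printed 0.91, 0.71, 0.49, 0.31, 0.17 and 0.08. The Simon rule (stop at 0 of 8, succeed at 4 or more of 18) gives type I error 0.093, power 0.906 and early stopping 0.430, as 14.6 states. Both are sound.

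**2. Patients at the level below the MAD after the table's rule.**

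| Already treated there | Added | Total |
|---|---|---|
| 1 (cleared in accelerated titration) | 3 | 4 |
| 3 (one standard cohort) | 3 | 6 |
| 6 | 0 | 6 |

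Only the first row falls short. Reaching six would need five added patients. With four at the MTD, stage 1 of phase II needs 8 − 4 = 4 more, not two.

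**3. When the first row applies.** It applies if the conversion level is level 2 or higher and becomes the MAD, or if a candidate level fails and de-escalation reaches a one-patient level. If conversion occurs at level 1, no one-patient level lies below it. If the MAD lies above the conversion level, the level below the MAD already holds three or six.

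**4. Chance that the conversion level becomes the MAD, given conversion there.** The protocol gives no DLT rates, so the true risk q for the added patients is an assumption. Two or more DLTs stop escalation, as in the bullets. The trigger is milder than a DLT, so the trigger patient may or may not have had one.

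- Trigger patient without DLT: 1 − [(1−q)² + 2q(1−q)⁴] = 0.37, 0.54, 0.69 at q = 0.30, 0.40, 0.50.
- Trigger patient with DLT: 1 − (1−q)⁵ = 0.83, 0.92, 0.97.

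For the gap to arise, conversion must be at level 2 or higher. These are not overall probabilities that it arises.

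**5. What four rather than six patients would mean.** A patient who cleared a level in accelerated titration had no trigger toxicity, so the first patient is taken as free of DLT. The level passes with at most one DLT among the added patients: P = (1−q)ⁿ + nq(1−q)ⁿ⁻¹, with n = 3 or n = 5.

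| True DLT risk (assumed) | At most 1 of 4 (n = 3) | At most 1 of 6 (n = 5) |
|---|---|---|
| 0.20 | 0.896 | 0.737 |
| 0.33 | 0.745 | 0.468 |
| 0.40 | 0.648 | 0.337 |
| 0.50 | 0.500 | 0.188 |

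**6. Precision.** 14.5 plans a 95% interval at each level. Exact intervals are 0–60.2% for 0/4, 0.6–80.6% for 1/4, 0–45.9% for 0/6 and 0.4–64.1% for 1/6.

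**The case against.** The best defense is that six is plainly intended. It appears in the exception clause of the MAD rows, in the MTD row, in the fourth bullet, and implicitly in 14.6. 14.3 also speaks of standard groups of at least three patients, so the three added patients could be read as the level's first standard cohort, to which the fourth bullet then adds up to three more. Nothing instructs the team to stop at four. A sensible team might well go to six unprompted.

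The point about intent stands, and it is why the repair is easy. The workable reading is not in the text, however. It needs the accelerated patient to be left out of the count, and the fourth bullet applies to a level where only three were treated, whereas this one would hold four. The instruction to study the previous level in the same fashion applies only after a candidate has failed, and gives no number for a one-patient level.

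Two stronger readings are tempting and should be resisted.

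- A reader might infer that the protocol itself predicts this path, because 5.2 says: "We predict that the DLT will occur around the third dose level since it is defined differently compared to the prior trials". That sentence predicts where DLT will occur. It does not say that levels 1 and 2 will clear on one patient each, or that level 3 will be both the conversion level and the MAD. Conversion needs only a grade 2 non-hematologic toxicity or delayed counts at day 22, so it may well happen below the MAD, where the rule works. The starting dose is also close to the earlier solid-tumor MTD, which makes early conversion plausible.
- A reader might infer that no MTD could be named. The third bullet and 14.5 would each supply one. The trouble is that they may do so on too few patients.

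**Conclusion.** The plan is wrong as written on one conditional path. Where the level below the MAD was cleared in accelerated titration, the stated expansion yields four patients against the six that the MTD row and fourth bullet require, while the third bullet and 14.5 would accept one to four. The count follows directly from 14.4.2 and needs no assumption.

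The size of the consequence does rest on assumptions: that the team accepts at most 1 DLT in 4, which no rule directs, and a true DLT risk that the protocol does not give. Under these, a level at 33/40/50% true risk passes with probability 0.75/0.65/0.50 rather than 0.47/0.34/0.19. The overall chance of meeting the path cannot be estimated from the documents.

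A reader might also infer damage to phase II from the mismatch with 14.6. The documents do not support that: 8 and 18 are stated outright, so type I error, power and the phase II sample size are untouched. The sponsor should make the change because the MTD is a primary aim and the phase II dose.

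**What to change.** - **14.4.2 table, both MAD rows:** in place of adding three, write *subjects will be added to reach six in total*, keeping the exception for a level that already has six.
- **14.4.2, fourth bullet:** apply it to a level with *fewer than six patients* and accrue to six in total.
- **14.4.2, third bullet:** call the previous level the *candidate MTD*, subject to that confirmation.
- **14.5:** add to the MTD definition *with at most 1 DLT in six patients*.

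The cost is up to two more patients per candidate level, since five rather than three are added to a one-patient level. At the 1–2 eligible patients per month in 14.8, that is about 1–2 months (2/2 to 2/1). These patients count toward the 8 and 18 in 14.6 only if the level is confirmed as the MTD. If it fails, the next level down must be filled as well. Six patients also reject an acceptable level more often than four: at an assumed 20% true DLT risk, 1 − 0.737 = 0.26 against 1 − 0.896 = 0.10. That is the price of the at-most-1-of-6 rule the plan already states.
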